## **Sample Size**

Based on our published data for knowledge of long-term outcomes, we expect average parent knowledge of seven long-term outcomes of 50% (SD 35%) in the ACOG group. In our population, English literacy is ~90% while ~80% possess smartphones. With 50 participants in each group, we can detect a 20% difference in knowledge, with power of 80% and  $\alpha$  of 0.05. To allow for 10% attrition, 55 pregnant participants will be enrolled in each group.

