**Study Title: Preemie Prep For Parents (P3): Home Antenatal Prematurity Education**

**NCT04093492**

**Original: 12/14/2018**

**Updated: 10/9/2023**

## STUDY RATIONALE

### Background

Obstetric (ACOG) and Pediatrics (AAP) practice guidelines recommend that parents at risk for premature birth receive information regarding premature birth and potential health outcomes. The NICHD 2014 Periviable Birth Joint Workshop concluded that the current process of providing information to parents at risk for premature birth needs improvements. Our proposal evaluates a new and substantively different approach to *when, where and how* prematurity education is provided to parents at risk for preterm birth. When: Anticipatory education is currently provided when the mother is in preterm labor, when time is short, and emotions run high. Our approach initiates education several weeks before the decision point. Where: Information is currently provided in the hospital, when families may be distracted or distressed and may not be together to discuss the information. Our approach provides information at home when parents can contemplate and discuss the information. How: Information is currently provided primarily verbally. Our approach provides multimedia information based on health literacy principles and developed by parents of preterm infants and experienced perinatal professionals.

**Preliminary studies:** Our previous work has informed the direction of the proposed work.

First, we prospectively assessed effectiveness of bedside verbal information by administering a questionnaire post-counseling to 49 women hospitalized for preterm birth. Notably, knowledge of short-term outcomes (lung immaturity, brain-bleed, infections, retinopathy, and nutrition) was higher (89% vs 53%) than knowledge of long-term outcomes (cerebral palsy, learning problems, behavior problems, chronic lung disease, blindness, and hearing impairment).

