Second, we developed a printed handout to augment verbal information. In an RCT of 60 women hospitalized for preterm birth, the control group received verbal information from a clinician and the intervention group additionally received a printed handout. Knowledge of long-term outcomes was higher in the intervention group, (71% vs 45%, P=0.02). This evidence-based printed handout was recognized in the 2015 American Academy of Pediatrics (AAP) Periviability Practice Guidelines. Despite benefit in limited trials, printed information has failed to have a wider impact due to difficulties in dissemination and scalability.

We then developed the P3 mobile education as multimedia information improves learning and digital tools decrease logistic challenges. Obstetricians in our hospital system introduced the P3 education to 31 parents at the time of diagnosis of a risk factor for preterm birth. The P3 mobile education was downloaded to the participant smartphone from Apple store or Google play. The median (range) GA at enrollment was 20 (18-22) weeks. Four weeks after enrollment, 28 participants (18 mothers and 10 fathers) completed the final survey. GA at birth is known for 15 of the 18 mothers, with 6 (40%) experiencing preterm birth between 22-36 weeks GA. Among the 15 participants for whom utilization data is available, over the 4 weeks of participation, the P3 mobile education was accessed for a total of 118.5 hours, with range of 6 minutes to 14 hours per participant. Participants reported receiving more information from the P3 mobile education than from their healthcare provider, in the areas of preterm labor, premature infants and parental role and responsibilities.

	Select survey items and participant responses	Yes (%)
Medical knowledge		
1. Did the app provide new information to you?		100
2. Was some of the information given in the app important for you to know?		100
3. Because of the app, do you feel better prepared if you were to have a premature infant?		100
4. In your opinion, will this app benefit families?		100
5. Did the app inform you about difficulties that a premature baby may face at birth?		89
Emotional health		
1. Did the app make you feel more aware of your risk for having a premature delivery?		93
2. Did the app increase your anxiety unnecessarily?		14
3. As time passed and you were familiar with the information provided, did the app increase your anxiety about having a premature infant later?		21

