#### Randomization

**1)** Pregnant women (or minors) who consent to participate will be randomized 1:1 to the P3 mobile education (intervention) or the link to electronic ACOG handout arm (active control), with assignment to be determined by REDCap displaying the computer-generated random assignment. Block randomization will be used with random block sizes of 2 and 4, based on the gestational age of the pregnant woman at the time of enrollment, with participants with baseline assessment during weeks 16-18 in one block, and those with baseline during weeks 19-21 in another block. A randomization list will be generated using the R package *blockrand*

**2)** Eligible partners who consent to participate will be assigned to the same intervention group as the pregnant participant, otherwise they will contaminate each other.

**3)** Participants will receive either links to ACOG education or be added as a user to the P3 mobile education site via email or text to their smartphone. The CRA will then provide a brief tutorial and the study team contact information.

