### **Data Analysis**

[name] will perform 1) blinded scoring of the Prematurity Knowledge Questionnaire using prespecified rules for each response, and 2) blinded analysis with masked group assignment in the dataset. The randomized design, the blinded scoring, and the blinded comparison of post-intervention NICHD recommended knowledge between the P3 and ACOG groups should achieve robust and unbiased results. The Educational-Aid Questionnaire responses and the P3 tracking data will be analyzed separately after completion of the other analyses.

Statistical analyses will be conducted in SAS. The primary outcome is the knowledge score for long-term outcomes (cerebral palsy, learning problems, behavior problems, chronic lung disease, blindness, and hearing impairment), and the primary analysis will use Student's t-test to compare the two groups on knowledge of long-term outcomes at 25 weeks. We will use regression methods to examine relationships between knowledge and sociodemographic characteristics, health literacy level, and the mobile intervention use pattern captured by the P3 software. Additional planned analyses will compare knowledge at later time points and in the other NICHD-recommended domains, e.g. short-term outcomes, as well as differences between groups in preparation for decision-making scores and anxiety scores. We will also use regression methods to examine relationships between knowledge and sociodemographic characteristics, health literacy level, and the mobile intervention use pattern captured by the P3 software.

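### Does sizing the trial on seven long-term outcomes, from an unnamed source, undermine the 80% power when the primary endpoint lists six?

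*Combined protocol and SAP*

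**What the plan says.** All references are to the combined protocol and SAP.

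- **Sample Size (Aim 1).** The inputs are introduced with "Based on our published data for knowledge of long-term outcomes", and the text continues "we expect average parent knowledge of seven long-term outcomes of 50% (SD 35%) in the ACOG group". It then says "With 50 participants in each group, we can detect a 20% difference in knowledge, with power of 80% and" a type I error of 0.05, and "To allow for 10% attrition, 55 pregnant participants will be enrolled in each group". No study is named.
- **Data Analysis (Aim 1).** "The primary outcome is the knowledge score for long-term outcomes (cerebral palsy, learning problems, behavior problems, chronic lung disease, blindness, and hearing impairment". That is six outcomes. The primary test is Student's t-test at 25 weeks. Scoring is blinded and follows rules fixed in advance, which the document does not reproduce.
- **Background, preliminary studies.** A questionnaire in 49 women found short-term knowledge "higher (89% vs 53%) than knowledge of long-term outcomes (cerebral palsy, learning problems, behavior problems, chronic lung disease, blindness, and hearing impairment", the same six. In a later randomised trial of 60 women, "Knowledge of long-term outcomes was higher in the intervention group, (71% vs 45%, P=0.02". Neither result is given with an SD.
- **Randomization.** Pregnant participants "will be randomized 1:1 to the P3 mobile education (intervention" or the ACOG handout.

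**The concern.** There are two grounds for doubt. First, the sample size refers to a seven-outcome score and the primary endpoint lists six. Taken literally, the score that was sized is not the score to be tested, and a reader cannot tell whether the denominator is six or seven. For a single primary endpoint, an open denominator could also leave room to choose items later.

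Second, the SD drives the power, and it cannot be traced. The two earlier studies show control-type means of 53% and 45%, not 50%, and no SD. The randomised trial's P value can also be read as pointing to an SD above 35%. If the true SD were 40% or 42%, power for 20 points with 50 per arm would be about 70% or 65%. The trial could then miss a difference that it says it can detect.

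**Working it through.** **Inputs.** From Sample Size (Aim 1): difference 20 points, SD 35% (taken as common to both arms), 50 analysed per arm, alpha 0.05 and 10% attrition. From Randomization: 1:1 allocation. The number of sides is not stated; two-sided is the version that reproduces the plan, since a one-sided test would need only 38 per arm.

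**1. The plan's own figure.**
- Normal approximation: n = 2 × (1.960 + 0.842)² × (35/20)² = 48.1, so 49 per arm.
- Noncentral t: n = 49.05, so 50 per arm.
- At 50 per arm the noncentrality is 20 / (35 × √(2/50)) = 20/7 = 2.86, and power is 80.8%. The detectable difference at 80% power is 19.8 points.
- Attrition: 55 × 0.9 = 49.5 per arm, with power 80.4%. Dividing 50 by 0.9 gives 55.6, so 55 is short by less than one person.

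The stated size and power reproduce.

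**2. Six items instead of seven.** The score is a percentage, so the 20-point difference keeps its meaning. Only the SD can move. For k exchangeable items, each correct with probability 0.5 and with inter-item correlation ρ, the variance of the score is 0.25 × (1 + (k − 1)ρ) / k.
- SD 0.35 with k = 7: ρ = (0.1225 × 7 / 0.25 − 1) / 6 = 0.405.
- With k = 6: SD = √(0.25 × (1 + 5 × 0.405) / 6) = 0.355.
- At SD 35.5%, power is 79.6% with 50 per arm, and 51 per arm would give 80%.

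A harsher bound scales the SD as if the items were uncorrelated: 35 × √(7/6) = 37.8%, power 74.5%. It contradicts the plan's own figure, because seven uncorrelated items at 50% would have an SD of √(0.25/7) = 18.9%, not 35%.

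**3. Is the 50% mean out of line?** The mean does not enter the t-test power formula; only the SD and the difference do. It also fits the earlier work. Pooling the 49 women at 53% with the trial's controls at 45%, and assuming 30 controls, gives (49 × 53 + 30 × 45) / 79 = 3947/79 = 49.96%. With 20 or 40 controls the result is 50.7% or 49.4%. The document does not say that the figure was obtained this way.

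**4. Does the randomised trial contradict SD 35%?** Assume that it supplied the SD, that 30 versus 30 were analysed, that the percentages are mean scores, and that P came from a two-sided t-test.
- With SD 35%: t = 26 / (35 × √(2/30)) = 2.88, P = 0.0056, not 0.02.
- P = 0.02 implies SD = 26 / (t₀.₉₉,₅₈ × √(2/30)) = 42.1%, and 40.2% to 43.8% over P from 0.015 to 0.025. Power for the present trial would be 65% (69% to 62%).
- The 95% sampling interval for that SD on 58 df is 35.6% to 51.4%. At P = 0.015 it is 34.0% to 49.1%.
- With fewer analysed, the implied SD falls: 38.2% at 25 per arm, 35.7% at 22 and 34.8% at 21.

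The Background gives only the total of 60 women. It does not state the split, the number analysed or the test.

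**The case for a change.** The strongest case is this. The primary outcome's list is closed, with nothing to mark it as illustrative, so seven against six is a contradiction about the denominator of the one primary endpoint. The SD is the input to which power is most sensitive, yet no study is cited for it, although the Aim 2 inputs carry a numbered reference. The team's own trial gives some reason to ask whether 35% is too low. Writing one list and naming one source would cost almost nothing.

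Part of this stands: the counts differ, no seventh outcome is named, and the SD has no identified source. What does not follow is that a different score was sized, or that any stated figure is wrong. Data Analysis is the section that governs the analysis, and it lists its items. Scoring is fixed in advance and blinded, which limits later item selection. The missing citation is weak evidence, since the only reference numbers in the text are 1, 19, 20 and 21, so others may have been lost in conversion. The inferred SD of 42% fails if the SD came from the 49-woman study, if P came from a rank test, or if about 21 or 22 per arm were analysed.

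**Conclusion.** No change to the plan follows. The seven-versus-six mismatch is a clerical slip worth about one point of power (80.8% to about 79.6%, assuming exchangeable items at 50% correct). It affects both arms alike. An analyst who follows the six outcomes listed under Data Analysis gets a valid comparison with essentially the planned power.

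The unnamed source for the SD is missing detail, not a shown error. Power does depend on that SD: at 50 per arm it is 91% for SD 30%, 81% for 35% and 70% for 40%. But nothing in the document establishes a value other than 35%, and the route to 42% needs several unstated facts at once. A misjudged planning SD would reduce power only. The t-test estimates its SD from the trial's own data, so the validity of the comparison would not suffer. Making the count agree and adding the citation would tidy the text without altering the design, the sample size or the analysis.

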## **Recruitment Feasibility**

Our institutional Clinical Research Data Warehouse 2016 clinic patient population shows: 303 pregnancies with hypertension and preeclampsia, 302 with fetal growth restriction, 218 with multiple gestations, 87 with shortened cervix, 80 with history of preterm labor, 68 with pre-existing diabetes, and 23 with cerclage. These

numbers indicate that goal recruitment is unlikely to be a problem. For the proposed study, we plan to enroll ~10 women (or minors) per month to reach our target enrollment within 1 year.

### **Data Management.**

All data will be stored securely at the Medical College of Wisconsin in REDCap. Personal identifiers will be kept separately, and only key personnel will have access to the identifiers. The P3 site is HIPPA compliant; however, we will not have PHI information on the P3 site as participants study ID numbers will be used.

### **Data Analysis**

[name] will perform 1) blinded scoring of the Prematurity Knowledge Questionnaire using prespecified rules for each response, and 2) blinded analysis with masked group assignment in the dataset. The randomized design, the blinded scoring, and the blinded comparison of post-intervention NICHD recommended knowledge between the P3 and ACOG groups should achieve robust and unbiased results. The Educational-Aid Questionnaire responses and the P3 tracking data will be analyzed separately after completion of the other analyses.

Statistical analyses will be conducted in SAS. The primary outcome is the knowledge score for long-term outcomes (cerebral palsy, learning problems, behavior problems, chronic lung disease, blindness, and hearing impairment), and the primary analysis will use Student's t-test to compare the two groups on knowledge of long-term outcomes at 25 weeks. We will use regression methods to examine relationships between knowledge and sociodemographic characteristics, health literacy level, and the mobile intervention use pattern captured by the P3 software. Additional planned analyses will compare knowledge at later time points and in the other NICHD-recommended domains, e.g. short-term outcomes, as well as differences between groups in preparation for decision-making scores and anxiety scores. We will also use regression methods to examine relationships between knowledge and sociodemographic characteristics, health literacy level, and the mobile intervention use pattern captured by the P3 software.

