##### Data collection. (Please see Survey Schedule in Section 52.)

At baseline (16-21 weeks) the CRA will administer the *health literacy assessment*, will ask participants to self-administer the *Entry Questionnaire*, an *anxiety measure*, and a subjective *global health measure*, and will abstract *maternal clinical data* and *reproductive history* from the medical record.

As pregnancy continues, REDCap will automatically send out questionnaires to participants at key time points: the start of their 25th, 30th, and 34th weeks. These times will include *Prematurity Knowledge Questionnaires* (specific to their gestational age), a *Preparation for Decision Making scale*, and an *anxiety measure*. At these time points, if they do not complete the questionnaire the first day they are sent it, they will

be sent an automatic reminder through REDCap for the next 2 days. If the participant still has not completed the questionnaire by this time, the CRA will contact the participant by phone.

At study completion, within two weeks of either preterm childbirth or completion of the 34 week questionnaire, participants will be asked to also complete the *Educational-Aid Questionnaire*.

Participants will receive \$20 for each completed follow-up assessment (up to \$80) and entered into a lottery to win an additional \$50 for every questionnaire they return the day they were sent it.

Data will be collected and managed using the REDCap (Research Electronic Data Capture) system. This system is a secure, web-based application designed to support data collection for research. It provides data validation, audit trails, and automated export procedures to statistical packages. Branching logic and calculated fields can also be created in the system to support data entry.

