## **Study Measures**

Apart from the Newest Vital Sign, all measures will be self-administered by participants.

The *Newest Vital Sign* is a validated health literacy scale that takes 3 minutes for a trained interviewer to administer. The participant is given a special ice cream label to review and is asked questions (by the CRA) to test understanding of words and numbers. Because it cannot be self-administered, this tool will only be used for the pregnant participant, as we know they will be in-person for intake.

The *Brief Health Literacy Screening* is a validated health literacy screening that in only one question is able to assess health literacy levels. This tool will be used with the partner participant, as it can be self-administered (unlike the Newest Vital Sign) and partners may not be present at the obstetrician appointment to enroll in-person.

The PROMIS Global Health scale is a measure of physical, mental, and social health. Its ten items are subjective self-report, and as such will be given to both the pregnant woman and her partner, though we have some information about the pregnant participants' health from her medical record.

The *Entry-Questionnaire* will collect information regarding socio-demographics, mobile technology use, family relationships, and participant's decision-making values.

The *Prematurity Knowledge Questionnaire* assesses knowledge of the information recommended by the NICHD panel for perivable birth. It consists of following knowledge domains: due date estimation, lowest GA necessary for survival, factors influencing preterm birth outcome, treatment options at perivable GA, long-term outcomes, short-term outcomes, and advocacy. It consists of a combination of fill-in-the-blank, multiple choice, and true/false questions. The items were evaluated and revised through cognitive interviews, which rely on intensive verbal probing of participants by a trained interviewer to identify otherwise unobservable problems with item comprehension, recall, and other cognitive processes that can be remediated through question rewording, reordering, or more extensive revision..

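### The primary 25-week t-test is valid and adequately powered, but it leaves out the gestational-age stratum used to randomise and the baseline health-literacy score, and so gives up modest precision if these predict knowledge

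*Combined protocol and SAP*

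**What the plan says.** Under Randomization, pregnant participants are allocated 1:1 in random blocks of 2 and 4 within two gestational-age groups: "participants with baseline assessment during weeks 16-18 in one block, and those with baseline during weeks 19-21 in another block". Under Data collection, health literacy and anxiety are both measured at baseline. Under Study Measures, the literacy instrument for the pregnant participants is the Newest Vital Sign: "this tool will only be used for the pregnant participant, as we know they will be in-person for intake".

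The primary comparison in Data Analysis (Aim 1) uses none of this: "the primary analysis will use Student's t-test to compare the two groups on knowledge of long-term outcomes at 25 weeks". Literacy enters only a separate exercise: "We will use regression methods to examine relationships between knowledge and sociodemographic characteristics, health literacy level". That sentence goes on to include the pattern of P3 use, which exists in one arm only, and it states no term for arm.

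The Aim 2 Data analysis section compares Preparation for Decision Making by t-test at each time point, also without the stratum. The Aim 1 section plans a between-group comparison of anxiety but names no method.

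**The concern.** Balancing on a variable by design and then ignoring it in the analysis leaves the variance it explains in the error term. If the stratum predicts the score, the t-test's standard error is slightly too large and the test slightly conservative. A baseline covariate that predicts the outcome also narrows the confidence interval when it is included, at almost no cost.

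Both variables are plausible predictors. The stratum sets how long a participant has had the materials when the 25-week questionnaire arrives, and the plan itself intends to study how literacy relates to knowledge.

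What is at stake is precision. The sample size is set close to its limit: "With 50 participants in each group, we can detect a 20% difference in knowledge, with power of 80" per cent, and "To allow for 10% attrition, 55 pregnant participants will be enrolled in each group". Covariates already in the database could cover attrition somewhat above plan.

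**Working it through.** **Inputs from the documents (Sample Size, Aims 1 and 2).** Difference 20 points; SD 35; α 0.05, taken as two-sided because sidedness is not stated; 50 analysed and 55 enrolled per arm. Aim 2: difference 0.6, SD 1.0.

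**Assumed.** R², the share of outcome variance explained by stratum and literacy together, is not in the documents and is shown as a range.

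**1. The plan's own figure.** The standard error is 35 × √(2/50) = 7.0 and the noncentrality is 20/7.0 = 2.857 on 98 df. Noncentral-t power is **80.8%**, which agrees with the stated 80%. The 95% half-width is 1.984 × 7.0 = 13.9 points.

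**2. The adjusted model.** The residual SD is 35 × √(1 − R²) and df are 96. Randomisation does not balance literacy exactly, so the variance is multiplied by the expected cost of chance imbalance, 48/47.5 = 1.0105.

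| R² | Residual SD | Power | 95% half-width |
|---|---|---|---|
| t-test | 35.0 | 80.8% | 13.9 |
| 0 | 35.0 | 80.3% | 14.0 |
| 0.05 | 34.1 | 82.3% | 13.6 |
| 0.10 | 33.2 | 84.3% | 13.3 |
| 0.20 | 31.3 | 88.2% | 12.5 |
| 0.30 | 29.3 | 92.0% | 11.7 |

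Adjusted power equals the t-test's at R² of about 0.011. If literacy alone supplies it, that is a correlation of √0.011, about 0.10. R² of 0.20 to 0.30 would need a correlation of 0.45 to 0.55.

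**3. Simulation check.** With stratified random blocks of 2 and 4, 100 analysed and 40,000 trials per setting, t-test and adjusted power were 80.9% and 80.4% at R² 0, and 80.5% and 84.1% at R² 0.10. With 10% of literacy scores missing and mean-imputed, at R² 0.10, they were 81.1% and 84.1%.

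**4. Attrition.** A fall from 55 to 49 per arm is 6/55 = 10.9%; a fall to 45 is 10/55 = 18.2%.

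| Analysed per arm | t-test power | R² needed for 80% when adjusted |
|---|---|---|
| 49 | 79.96% | 0.012 |
| 48 | 79.1% | 0.033 |
| 47 | 78.3% | 0.054 |
| 46 | 77.4% | 0.075 |
| 45 | 76.5% | 0.095 |

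At 45 per arm, adjustment with R² 0.10 gives 80.2%.

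**5. The stratum alone.** A 10-point difference between equal strata gives R² = 5²/35² = 0.020. The t-test's actual α is then 2 × [1 − Φ(1.96/√0.980)] = 4.8% instead of 5.0%.

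**6. Secondary outcomes.** Preparation for Decision Making: 84.4% power unadjusted, and 85.1% if the stratum explains 2% (97 df). Anxiety, assuming that the PROMIS reference SD of 10 applies here: the half-width is 3.97 T-score points unadjusted. With adjustment for the baseline score it is 3.99, 3.81, 3.46 and 2.85 at assumed baseline correlations of 0, 0.3, 0.5 and 0.7.

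**The case against.** The strongest reply is that nothing is broken. A prespecified unadjusted t-test is acceptable in a 110-person trial, it controls type I error, and it meets its stated power. The benefit depends on an R² that the documents never give: at 0.05 the gain is 1.5 power points (82.3% against 80.8%), and below about 0.011 there is a small loss. Power of 79.96% at 49 per arm rounds to the planned 80%, and 45 per arm implies attrition that the plan does not expect. All of this stands, and it limits the point to efficiency. It does not remove the point, because the possible loss is about 0.4 of a power point and the covariates are already collected.

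A second reply concerns timing. The document is dated December 2018 and updated October 2023, so replacing the primary test could be post hoc. Masked labels alone do not prevent that, since an A-versus-B difference can be seen without unmasking. This is right, and the fix is conditioned on it.

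A third is that no section says outright that the Newest Vital Sign precedes allocation. The plan places it at baseline, so this needs one clarifying sentence.

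Finally, the Aim 1 regressions are loosely specified and might include arm. They might, but no arm term is stated, so they do not amount to a planned adjusted comparison.

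**Conclusion.** The point holds as a modest and conditional loss of precision. The t-test is valid and adequately powered on the plan's assumptions. Adjusting for stratum and literacy would raise power from 80.8% to about 82% to 84% if together they explain 5% to 10% of the variance, and would lower it to 80.3% if they explain nothing. The higher figures in the table are illustrative only. At 47 to 49 per arm, an R² of about 0.01 to 0.05 is enough to keep 80% power; at 45 per arm it takes about 0.095. The stratum alone adds very little, and most of any gain would have to come from literacy.

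These results rest on SD 35, a two-sided test and the assumed R². Adjustment does not address bias from missing 25-week scores.

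**What to change.** - Make the primary analysis a linear model of the 25-week long-term-outcome score on arm, gestational-age stratum as randomised and baseline Newest Vital Sign score, by assigned arm in pregnant participants. Keep the t-test as a sensitivity analysis.
- Do this only if no outcome result by group has been seen, even under masked labels. Otherwise leave the t-test as primary and report the adjusted model as the sensitivity analysis.
- State that the Newest Vital Sign is completed before allocation, and give a rule such as mean imputation so that a missing literacy score drops nobody.
- Add the stratum to the Preparation for Decision Making comparison. Analyse anxiety by ANCOVA on the baseline PROMIS T-score plus stratum.
- Before coding the stratum, reconcile the 14-21 week enrolment window under Sample with the 16-21 week baseline under Randomization and Data collection; weeks 14 and 15 currently have no stratum.

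The cost is a few lines of SAP text and SAS code, with no new data and no extra participants. The statistical cost is at most about 0.4 of a power point. If results have already been seen, the cost is one added sensitivity analysis.
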